Categorical variables will be described by their absolute and relative frequency. Continuous variables will be described with total n, valid n, n unavailable, means, standard deviation, quartiles, minimum and maximum. Survival analysis will be performed using the Kaplan Meier method. A Cox regression model will be carried out to find independent variables associated with overall survival or time until disease progression.

Milestones

• Expected date of approval by the central IEC: 31 May 2025

• Expected date of opening of the first site: 01 June 2025

• Start recruitment: 01 June 2025

• End recruitment: 30 November 2026

• Recruitment period: 18 months

• Expected date for closing of data collection: 30 November 2027

• Interim Analysis after 18m of FUP of first 50 patients included: 30 April 2027

Expected date of final study report: 31 May 2028

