8. RESEARCH QUESTION AND OBJECTIVES

Research question

 What is the spectrum of adverse events and mitigation strategies associated with lorlatinib as a first line treatment in an ALK+ NSCLC real-world Spanish population?

Primary Objective

• To describe all the spectrum of the adverse events (AEs) of Lorlatinib (CTCAE v6.0) and its mitigation strategies, with special interest in CNS AEs

Secondary Objectives

- To identify factors that are predictive of AEs, with special interest in CNS AEs
- To evaluate the effectiveness of 1L lorlatinib in real-world practice
 - 1. rwPFS rate at 12 and 18 months in the ITT population with and without brain metastasis at baseline.
 - 2. rwDuration of Response (DoR)

- 3. rwDuration of Treatment (DoT)
- 4. rwTime to next therapy/treatment (TTNT)
- 5. rwSystemic and intracranial Objective Response rate (ORR) using Response Evaluation Criteria in Solid Tumors (RECIST v1.1.) criteria
- 6. rwTime to intracranial progression rate at 12 and 18 months with and without brain metastasis at baseline
- 7. rwCumulative incidence of brain metastases (BM) in ITT population at 12 and 18 months (with and without baseline BM)
- 8. rwOverall survival (OS) rate at 12 and 18m
- To evaluate the impact of lorlatinib on patients' quality of life
- To describe ALK testing methods used

Exploratory Objectives (up to 30 patients)

• To identify neuroimaging markers (MRI) that are predictive of the occurrence of CNS AEs

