2. rwDuration of Response (DoR)	2. To determine real world duration of response (DOR), as the time from the first occurrence of a documented objective response to disease progression or death from any cause, whichever occurs first, as determined by the investigator according to RECIST v1.1. criteria (or Time from first documentation of CR or PR (whichever occurs first) after index until death or PD)			
3. rwDuration of Treatment (DoT)	3. To determine duration of treatment (DoT) as the time from lorlatinib's first dose to last dose for any cause. (Time to treatment discontinuation or Time from first dose to last dose of a treatment)			

4.	rwTime to next therapy/treatment (TTNT)	4.	To determine Time to next therapy/treatment (TTNT) as the Time from end of lorlatinib treatment to institution of next therapy	
5.	rwSystemic and intracranial Objective Response rate (ORR) using RECIST v1.1. criteria.	5.	To determine the systemic and real-world intracranial objective response rate (ORR) as determined by the investigator using RECIST v1.1. criteria	
6.	rwTime to intracranial progression rate at 12 and 18 months with and without brain metastasis at baseline	6.	Real world Time to intracranial progression rate at 12 and 18 months with and without brain metastasis at baseline	
7.	rwCumulative incidence of brain metastases (BM) in ITT population at 12 and 18 months (with and without baseline BM)	7.	Real world Cumulative incidence of brain metastases (BM) in ITT population at 12 and 18 months (with and without baseline BM)	
8.	rwOverall survival (OS) rate at 12 and 18m	8.	To determine the real-world overall survival (OS) rate at 12 and 18 months. OS is defined as the time from enrollment to death from any cause	
To evaluate the impact of lorlatinib on patients' quality of life.		of Pl Lo ar	hange from baseline in health-related quality f life (HRQoL), using the EORTC C30, RO_CTCAE (for CNS AEs) and submodules C13 at baseline, C1D15, C2D1, C3D1, C6D1 and every 3 months until the 1st year and then very 6 months	
To describe ALK testing methods used		Describe the different methods used to testing ALK mutations		
Exploratory Objectives (up to 30 patients)			Corresponding Endpoints	
To identify neuroimaging markers (MRI) that are predictive of the occurrence of CNS AEs		Fazekas scale, morphometric and radiomic analysis of baseline magnetic resonance images (MRIs) to identify imaging markers associated with the development of CNS AEs		

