9.2. Setting

The study population includes adult patients aged 18 years or older diagnosed with non-small cell lung cancer who are carriers of the ALK gene rearrangement recruited in an 18-month estimated period from 20 high specialized hospitals at the country level who have started first-line therapy with lorlatinib according to label prescription, with treatment duration of at least 7 days and up to 28 days.

In Spain, molecular diagnosis of ALK rearrangement is routinely performed in patients with non-small cell lung cancer according to the diagnostic guidelines of the Spanish Society of Pathological Anatomy and the Spanish Society of Medical Oncology. Only patients with a confirmed and valid ALK testing will be included in our cohort. Among validated testing methods are the following: FISH fluorescence in situ hybridisation (FISH) Immnunohistochemistry using the D5F3 clon Roche VENTANA (IHC) mainly, PCR polymerase chain reaction (PCR) and the next generation sequencing (NGS)²³.

Given the estimated low incidence rate of 3.4% for this disease among the local population¹⁵, and the difficulty of performing molecular testing in some hospitals at the country level, the

Principal Investigators decided to involve centers specializing in the molecular diagnosis of ALK because otherwise, the lack of expertise in the molecular diagnostics would negatively impact the number of patients that can be enrolled in the study.

Based on data from the CROWN trial, where the incidence of CNS AEs was reported to be 42%, and assuming that the incidence could be higher in real clinical practice but potentially under-detected or recorded as grade 1 cases, they estimated that 116 patients treated with lorlatinib in first-line therapy for ALK+ non-small cell lung cancer are needed. This would provide 80% power to detect an incidence of 55% any grade CNS AEs using a 2-sided test.

Data collection Periods

Patient data will be collected in the following periods:

- **Pre-index period**: since diagnosis to start lorlatinib treatment.
- Index Date: date of start of lorlatinib.
- Post-index period: visits performed under clinical practice since index date and until
 end of study period

Patient data collection will cease at the end of study completion.

Study Visits

The study will be conducted in 5 visits, according to clinical practice:

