9.3. Variables

Variable	Role	Data source(s)	Operational definition
Safety			
· //		Investigators Patient clinical record/Electronic Health record (EHR)	 Adverse Event: An AE is any untoward medical occurrence in a patient administered to a medicinal product. Serious Adverse Event: An SAE is any untoward medical occurrence in a patient administered a medicinal or nutritional product (including pediatric formulas) at any dose that: Results in death Is life-threatening Requires inpatient hospitalization or prolongation of hospitalization (see below for circumstances that do not constitute SAEs) Results in persistent or significant disability/incapacity (substantial disruption of the ability to conduct normal life functions) Results in congenital anomaly/birth defect

Variable	Role	Data source(s)	Operational definition
rwPFS rate at 12 and 18 months in the ITT population with and without brain metastasis at baseline.	Outcome measures	Investigators Patient clinical record/Electronic Health record (EHR)	To determine real-world progression-free survival (rwPFS) defined as the time from enrollment to the first occurrence of disease progression (intracranial or systemic) or death from any cause, whichever occurs first, as determined by the investigator using RECIST v1.1. criteria, at 12 and 18 months, in the ITT population with and without brain metastasis at baseline
rwDuration of Response (DoR)	Outcome measures	Investigators Patient clinical record/Electronic Health record (EHR)	To determine real world duration of response (DOR), as the time from the first occurrence of a documented objective response to disease progression or death from any cause, whichever occurs first, as determined by the investigator according to RECIST v1.1. criteria (or Time from first documentation of CR or PR (whichever occurs first) after index until death or PD)
rwDuration of Treatment (DoT)	Outcome measures	Investigators Patient clinical record/Electronic Health record (EHR)	To determine duration of treatment (DoT) as the time from lorlatinib's first dose to last dose for any cause. (Time to treatment discontinuation or Time

Variable	Role	Data source(s)	Operational definition
			from first dose to last dose of a treatment)
rwTime to next therapy/treatment (TTNT)	Outcome measures	Investigators Patient clinical record/Electronic Health record (EHR)	To determine Time to next therapy/treatment (TTNT) as the Time from end of lorlatinib treatment to institution of next therapy

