10.3. Patient Withdrawal

Patients may withdraw from the study at any time at their own request, or they may be withdrawn at any time at the discretion of the investigator or sponsor for safety, behavioral, or administrative reasons. In any circumstance, every effort should be made to document patient outcome, if applicable. The investigator would inquire about the reason for withdrawal and follow-up with the patient regarding any unresolved adverse events.

If the patient withdraws from the study, and also withdraws consent for disclosure of future information, no further evaluations should be performed, and no additional data should be collected. The sponsor may retain and continue to use any data collected before such withdrawal of consent.

Withdrawal criteria: Patients will receive the study treatment while it is considered to be in their best interest. Specifically, individual treatment of a given patient will continue until:

- Documented disease progression.
- Unacceptable toxicity after allowed dose reductions.
- Intercurrent illness of sufficient magnitude to preclude safe continuation of the study treatment.
- Patient's refusal (follow-up has to be continued for those patients who refuse treatment, but do not withdraw consent) and/or non-compliance with study requirements.
- A major protocol deviation that may affect the risk/benefit ratio for the participating patient.

- Requirement of > 2 dose reductions.
- Investigator's decision.

Patients who are withdrawn for any reasons must not be re-treated in the context of this study at any time. However, if the only reason for discontinuation is disease progression, the patient can be treated beyond radiological progression provided the patient is obtaining benefit from the treatment with good tolerance to the treatment, and the patient and sponsor agrees with the decision.

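### rwTTNT is clocked from the end of lorlatinib, so it measures the gap between treatments rather than first-line effectiveness, and patients still on lorlatinib have no value

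*Protocol*

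**What the plan says.** Section 8 places rwTTNT fourth of eight measures under the secondary objective "To evaluate the effectiveness of 1L lorlatinib in real-world practice".

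The endpoint table in Section 9.1 defines it: "To determine Time to next therapy/treatment (TTNT) as the Time from end of lorlatinib treatment to institution of next therapy". The variables table in Section 9.3 gives the same origin and event: "Time from end of lorlatinib treatment to institution of next therapy". No other section gives a different origin.

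The item just above it in Section 9.1 is duration of treatment: "To determine duration of treatment (DoT) as the time from lorlatinib's first dose to last dose for any cause".

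Section 9.2 defines the index date as the "date of start of lorlatinib", but the rwTTNT definition does not use it.

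**The concern.** A measure of how well first-line lorlatinib works should lengthen when lorlatinib controls disease for longer. This one cannot, because its clock starts only after the last dose. What it captures is how quickly the next therapy follows. A longer value is not clearly better: it may reflect delay, frailty or a lack of options.

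The end of lorlatinib is not a clean marker of failure either. Section 10.3 states that, where progression is the only reason for discontinuation, "the patient can be treated beyond radiological progression provided the patient is obtaining benefit from the treatment". If the next therapy starts before the last lorlatinib dose, the interval is zero or negative.

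The definition also restricts the endpoint to patients who have stopped. Those still on treatment at data closure, who are doing best on this measure, drop out. The result would be reported as effectiveness but would describe a subgroup selected by having ended treatment.

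**Working it through.** The protocol states no figure for rwTTNT, so there is none to reproduce. The check compares time origins, then estimates how many patients would have a time zero.

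**1. Time origin**

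| Measure | Clock starts | Clock ends |
|---|---|---|
| Duration of treatment (9.1) | first lorlatinib dose | last lorlatinib dose |
| rwTTNT as written (9.1, 9.3) | end of lorlatinib | start of next therapy |
| rwTTNT from the index date | first lorlatinib dose | start of next therapy |

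The third row is the sum of the first two. As written, rwTTNT keeps only the gap and discards the part that reflects lorlatinib.

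Two illustrative patients, each with a one-month gap:

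- Stops at month 6: 1 month as written; 6 + 1 = 7 months from the index date.
- Stops at month 24: 1 month as written; 24 + 1 = 25 months from the index date.

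**2. Patients with a time zero at data closure**

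Inputs from the protocol:

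- Milestones in the abstract: "Start recruitment: 01 June 2025", recruitment ends 30 November 2026, data collection closes 30 November 2027. Follow-up therefore runs from about 12 months (last patient) to about 30 months (first patient).
- Section 7: treatment duration with lorlatinib in the pivotal trial, median 57.0 months, lower quartile 13.9 months.
- Section 9.5: 116 patients.

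Assumptions: accrual is uniform over 18 months, nobody is lost to follow-up, and discontinuation follows the pivotal-trial durations.

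For a constant discontinuation hazard λ, the average proportion stopped over follow-up uniform on 12 to 30 months is

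1 − [exp(−12λ) − exp(−30λ)] / (18λ).

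- **Exponential with median 57.0 months.** λ = ln 2 / 57.0 = 0.01216. Proportion = 1 − (0.8642 − 0.6943)/0.2189 = 0.224. 116 × 0.224 ≈ 26 stopped.
- **Piecewise exponential through both figures.** Hazard −ln(0.75)/13.9 = 0.02070 up to 13.9 months, then −ln(0.50/0.75)/(57.0 − 13.9) = 0.00941. Averaging numerically over 12 to 30 months gives 0.297. 116 × 0.297 ≈ 34 stopped.
- **Exponential through 25% at 13.9 months.** λ = −ln(0.75)/13.9 = 0.02070. Proportion = 1 − (0.7801 − 0.5375)/0.3725 = 0.349. 116 × 0.349 ≈ 40 stopped.

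So about 26 to 40 of 116 (22% to 35%) would have a time zero. The other 76 to 90 (about 65% to 78%) would not. The number with an observed interval would be smaller still, since some who stop will have no further therapy. Measured from the index date, all 116 contribute.

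**The case against.** **It is a secondary, descriptive measure.** Sections 9.1 and 9.9 call the study descriptive, the primary objective is adverse events, and the sample size rests on the incidence of CNS adverse events. No hypothesis or decision depends on rwTTNT. This stands and limits the severity. It does not rescue the definition, because a descriptive estimate must still describe what its objective names.

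**Other endpoints keep the information.** Duration of treatment, rwPFS and OS all separate early from late failures. This also stands: the study does not lose the information, but this one endpoint does not carry it.

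**Restriction to a post-baseline subset is not disqualifying in itself.** Duration of response is also defined only for a subset. That is fair. The difference is that duration of response still measures benefit within its subset, whereas this interval excludes the treatment period altogether.

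**The SAP can settle it.** Section 9.7 assigns outcome definitions, missing data and censoring to the SAP. A reader might therefore infer that death without next therapy is an omission here; it is not, because that rule may properly sit in the SAP. The time origin is different: the protocol fixes it, in two places. Section 9.7 promises an amendment only for major changes to primary endpoints, so a correction made in the SAP alone would leave the two documents in conflict.

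**The change might look free.** A reader might infer that every date needed is already collected. The documents do not show this. Section 9.3 lists post-progression treatment as yes/no, type and description, and the data collection overview in Section 9.2 lists its type, at the final visit. Neither names a start date.

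**Conclusion.** The definition is wrong as written for the objective it serves. It measures the gap between treatments, has no clear direction of benefit and has no time zero for patients still on lorlatinib. That follows from the wording alone and needs no assumption about rates.

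The size does rest on assumptions. If discontinuation resembles the pivotal trial, about 65% to 78% of the 116 patients would have no value. The study's own discontinuation rate is unknown, so no single count within 26 to 40 stopped should be read as a forecast.

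Severity is moderate. A reader might infer that the error undermines the study, but it affects one of eight secondary effectiveness measures, and the primary safety objective and N = 116 are untouched. A reader might also infer that the result will be misread against published time-to-next-treatment figures. The protocol cites no such comparator, so the point does not rely on that.

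**What to change.** In the endpoint table of Section 9.1 and the variables table of Section 9.3, define rwTTNT as the time from the index date (first lorlatinib dose) to the start of the next systemic anticancer therapy, estimated in all patients. Patients without a next therapy are censored at last contact. The handling of death, as part of a composite event or as a competing risk, can be set in the SAP. Saying systemic matters because the post-progression treatment types in Section 9.3 include radiotherapy and palliative care.

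If the stop-to-next-therapy gap is of interest, report it under a separate name, such as treatment-free interval, as a description among patients who stop.

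The cost is two table entries and one check of the eCRF: confirm that it records the start date of the next therapy whatever the reason for switching. The listed fields are labelled post-progression, so a switch for toxicity without progression has no clearly listed place. The start and end dates of lorlatinib are already among the variables.

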- 1. **Baseline visit:** the day on which the patient fulfils the inclusion and exclusion criterion, including signature of the Informed Consent (i.e. the day on which the prospective observation starts) (within cycle 1 if lorlatinib)
- 2. Follow-up visit 1: will be scheduled at month 3 (third cycle of Iorlatinib)
- 3. Follow-up visit 2: will be scheduled at month 6 (sixth cycle of Iorlatinib)
- 4. Follow-up visit 3: Follow-up visit at month 12 (twelfth cycle of lorlatinib)
- 5. Final Visit: end of follow-up (end of data collection expected November 2027)

Data collection overview

Study Visits and Assessments	Baseline			FU3 C12D1	Final Visit
Informed consent	X				
SOCIO DEMOGRAPHIC DATA					
Medical history	X				
Physical examination including Height and weight	X	X	X	X	X

Study Visits and Assessments	Baseline	FU1	FU2	FU3	Final
		C3D1	C6D1	C12D1	Visit
Previous personal and family history of cancer	X				
CLINICAL DATA					
ECOG	X	X	X	X	X
Laboratory: Hematology and Blood chemistry (dyslipemia profile included). According to routine clinical practice	X	X	X	X	X
Comorbidities since Index Date: Charlson Index	X	X	X	X	X
Concomitant treatment(s) including previous history of Thromboembolic Disease	X	Х	X	X	X
Information of baseline tumor diagnosis: date, staging, (TNM),biopsy, PD-L1 expression, other mutations, etc	X				
Information regarding advanced disease: date, staging, metastatic location, CNS metastasis, previous systemic chemotherapy, radiotherapy, etc	X				
Previous systemic chemotherapy (Yes/No)	X				
Assessments CT scan	X				
Assessments brain MRI	X				
LORLATINIB TREATMENT					
Start, Stop and Discontinuation date	X	X	X	X	X
Dose by cycle	X	X	X	X	X
Reason for discontinuation or for dose reduction	X	X	X	X	X
Evaluation of Treatment Response: method (CT scan, MRI, others) and response	х	Х	X	X	X
AFTER LORLATINIB TREATMENT					

Study Visits and Assessments		FU1	FU2	FU3	Final
		C3D1	C6D1	C12D1	Visit
Post-progression treatment: type and palliative care					X
Date of death or last follow-up or last contact					X
QUALITY OF LIVE					
EORTC QLQ C30, LC13	X	X	X	X	X
SAFETY					
PRO-CTCAE	X	X	X	X	X
Adverse Events	X	X	X	X	X

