9.2.1. Inclusion Criteria

Patients must meet all of the following inclusion criteria to be eligible for inclusion in the study:

- Evidence of histologically or cytologically confirmed diagnosis of locally advanced and/or metastatic NSCLC (Stage IV, AJCC v8.0) harboring an ALK rearrangement identified by an approved diagnostic test. (FISH, IHC, RT PCR, Next generation sequencing, NGS)
- 2. Patients aged ≥18 who have initiated first-line therapy with lorlatinib at least 7 days and up to 28 days prior to enrolment in the study according to routine clinical practice.
- 3. ALK+ patients with intracranial and extracranial disease are allowed.
- 4. Patients should have a minimum of 3 months predetermined data recorded in their medical records.
- 5. Informed consent form personally signed and dated stating that the patient (or their legal representative) has been informed of all relevant aspects of the study.
- 6. ECOG performance status 0-2.
- 7. No previous treatment with an ALK TKI (alectinib, brigatinib, ceritinib, crizotinib. Other systemic treatments if previous relapse in early stages are allowed.

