Height at tumor progression	patient's characteristics	Investigators Patient clinical record/Electronic Health record (EHR)	• Meters
Weight at tumor progression	patient's	Investigators Patient clinical record/Electronic Health record (EHR)	• kg
Post-progression treatment	patient s	Investigators Patient clinical record/Electronic Health record (EHR)	• Yes/No
Post progression treatment Type	patient's characteristics	Investigators Patient clinical record/Electronic	Chemotherapy, TKI (specify type), Immunotherapy,

Variable	Role	Data source(s)	Operational definition
		Health record (EHR)	Radiotherapy, Palliative Care.
Post progression treatments	On-treatment patient's characteristics		Describe subsequent treatment
Clinical data after lorlatinib completion			
Alive: Yes/No	After- treatment data	Investigators Patient clinical record/Electronic Health record (EHR)	• Yes/No
Date of death or last follow-up	After- treatment data	Investigators Patient clinical record/Electronic Health record (EHR)	Date format

Variable	Role	Data source(s)	Operational definition
Participant's perspective			
EORTC QLQ-C30	Outcome measure	Baseline, C3D1, C6D1, C12D1, Final visit	ePRO (through mobile device) questionnaire containing 30 questions and assesses the quality of life of oncological participants multidimensionally over 10 subscales.
EORTC QLQ-LC13	Outcome measure	Baseline, C3D1, C6D1, C12D1, Final visit	ePRO (through mobile device) questionnaire for lung participants. The QLQ-LC13 incorporates one multi-item scale to assess lung cancerassociated symptoms (i.e.coughing, haemoptysis, dyspnoea and pain) and side- effects from conventional chemo- and radiotherapy.
PRO-CTCAE (only for CNS AEs)	Outcome measure	Baseline, C3D1, C6D1, C12D1, Final visit	ePRO (through mobile device) questionnaire. When referring to CNS (Central Nervous System) adverse events, the PRO-CTCAE helps in assessing symptoms such as headaches, dizziness, and cognitive changes, which are crucial for understanding the impact of cancer treatments on the nervous system.

Variable	Role	Data source(s)	Operational definition
Exploratory variables (30 patients expected)			
To identify neuroimaging markers (MRI) that are predictive of the occurrence of CNS AEs	Exploratory analysis	MRI	Fazekas scale, morphometric and radiomic analysis of baseline magnetic resonance images (MRIs) to identify imaging markers associated with the development of CNS AEs.

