Only variables obtained according to routine clinical practice that follow objectives can and should be documented in this study and follow objectives.

To describe the safety profile of lorlatinib in the patients under the study, the following variables will be collected:

- AE, serious adverse events (SAE), and treatment-associated mortality.
- Time to onset and duration of AEs

Adverse events included in the study database will be coded according to CTCAE v6.0.

To study the safety profile, all adverse events that have been identified since the start of treatment with lorlatinib and related to the drug will be collected in the CRF. (More detail in section 11).

Researchers are reminded of their obligation to notify adverse reactions that the Pharmacovigilance Center as they are aware of.

Quality of Life (QoL) Assessments

Scales will be completed by patients at each study visit:

- EORTC QLQ C30: is a cancer-specific quality of life questionnaire (QLQ-C30), which consists of five functional scales (physical, role, cognitive, emotional, and social); nine symptom scales (fatigue, pain, nausea and vomiting, dyspnea, loss of appetite, insomnia, constipation, diarrhea, and financial difficulties); and a global health status/quality of life (GHS/QoL). Based on 30 questions in total, the scores range from 0 to 100. This questionnaire was approved and psychometrically validated (as well as each of its translations).
- QLQ LC13: the EORTC QLQ-LC13 is a supplementary questionnaire specifically designed for lung cancer patients. It is used in conjunction with the EORTC QLQ-C30 to assess the quality of life in these patients. The QLQ-LC13 focuses on lung cancer-specific symptoms and treatment side effects, such as coughing, shortness of breath, pain, and side effects from chemotherapy¹⁰.

• PRO-CTCAE (for CNS AEs)¹¹: is a tool developed by the National Cancer Institute (NCI) to capture symptomatic adverse events directly from patients receiving cancer treatment. It includes a set of questions that patients can answer to report the severity, frequency, and interference of symptoms they experience. When referring to CNS (Central Nervous System) adverse events, the PRO-CTCAE helps in assessing symptoms such as headaches, dizziness, and cognitive changes, which are crucial for understanding the impact of cancer treatments on the nervous system.

Exploratory variables (30 patients expected)

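### The quality-of-life baseline is taken 7 to 28 days into treatment, and the protocol gives two conflicting questionnaire schedules

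*Protocol*

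**What the plan says.** The objective in Section 8 is "To evaluate the impact of lorlatinib on patients' quality of life". The objectives and endpoints table in Section 9.1 turns this into change from baseline on the EORTC QLQ-C30, the LC13 module and the CNS items of PRO-CTCAE, collected "at baseline, C1D15, C2D1, C3D1, C6D1 and every 3 months until the 1st year" and every six months afterwards.

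Section 9.2 says "The study will be conducted in 5 visits, according to clinical practice". Its data collection table marks the questionnaires at baseline, C3D1, C6D1, C12D1 and the final visit. Section 9.3 repeats that list for each of the three instruments, "Baseline, C3D1, C6D1, C12D1, Final visit", and adds "Scales will be completed by patients at each study visit".

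Section 9.2 defines the baseline visit as the day on which eligibility is met and consent is signed, that is "the day on which the prospective observation starts) (within cycle 1 if lorlatinib". Inclusion criterion 2 requires lorlatinib to have started "at least 7 days and up to 28 days prior to enrolment". Section 9.2 defines the index date separately, as the start of lorlatinib. The last visit is given as "Final Visit: end of follow-up (end of data collection expected November 2027".

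**The concern.** A change score answers a question about the treatment only if its starting value precedes the treatment. Here the starting value follows one to four weeks of drug. Early symptomatic benefit, and early CNS symptoms on PRO-CTCAE, may already be in it. The amount of prior exposure also differs between patients. Reported as the impact of lorlatinib, the result would be read as change from the untreated state, which it is not.

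Separately, sites and the electronic questionnaire build cannot follow both schedules. The choice decides whether anything is collected between enrolment and C3D1, and whether there are fixed-time assessments after about a year. This matters because Section 9.5 argues that CNS events are under-detected, most being grade 1. Questionnaires that were never issued cannot be recovered later.

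**Working it through.** The protocol attaches no figure to this endpoint, so there is none to reproduce. The check is a day count from the first dose. Cycle length is not stated; 28 and 30 days are assumed throughout.

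**Is any questionnaire taken before the first dose?**
- The baseline visit is the enrolment day (9.2), and enrolment is 7 to 28 days after the first dose (criterion 2).
- Section 10.2 requires consent before study-specific activity, unless a waiver is granted, and Section 9.2 places consent at the baseline visit.
- No section provides a pre-dose questionnaire.
- Prior exposure at the reference value therefore ranges from 7 to 28 days: 28/7 = 4-fold.
- C3D1 is 2 × 28 = 56 or 2 × 30 = 60 days after the first dose. The share of that time already past at baseline is 7/56 = 12.5% to 28/56 = 50%, or 7/60 = 12% to 28/60 = 47%.

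**How many time points does each schedule contain?**
- Sections 9.2 and 9.3: five.
- Section 9.1 with 12 months of follow-up: baseline, C1D15, C2D1, C3D1, C6D1, month 9, month 12 = 7.
- Section 9.1 with 30 months: add months 18, 24 and 30 = 10.
- The 12 to 30 months come from recruitment between June 2025 and November 2026 and data collection ending in November 2027. They apply to patients followed to the administrative end.

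**Is C1D15 a post-baseline point?** It falls 14 days after the first dose. Enrolment can fall on any of 28 − 7 + 1 = 22 days.

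| Enrolment, days after first dose | Number of days | C1D15 relative to baseline |
|---|---|---|
| 7 to 13 | 7 | after |
| 14 | 1 | same day |
| 15 to 28 | 14 | before |

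C2D1 is 28 or 30 days after the first dose. It follows baseline on 21 of the 22 days with 28-day cycles (same day for the last) and on all 22 with 30-day cycles.

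**When is the first post-baseline questionnaire under 9.2/9.3?** It is C3D1. The shortest gap is 56 − 28 = 28 days and the longest is 60 − 7 = 53 days.

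**Do the visit labels agree?** Section 9.2 calls the follow-up visits months 3, 6 and 12 but tabulates them as C3D1, C6D1 and C12D1. Day 1 of cycle k falls (k − 1) × cycle length after the first dose:

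| Visit | Days after first dose | Months (30.4 days) | Label in 9.2 |
|---|---|---|---|
| C3D1 | 56 to 60 | 1.8 to 2.0 | month 3 |
| C6D1 | 140 to 150 | 4.6 to 4.9 | month 6 |
| C12D1 | 308 to 330 | 10.1 to 10.8 | month 12 |

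**The case against.** The case for the plan is that this is a descriptive, non-interventional study without a comparator. Enrolling after the prescribing decision is a normal feature of such a study, and even a pre-dose baseline would not isolate a drug effect. Section 9.7 leaves outcome definitions, scoring and missing data to the SAP. Much of this stands: enrolment after the start of treatment is defensible, and the SAP can define the change score. But a SAP cannot supply questionnaires that were not collected, and it should not have to decide which of two protocol schedules the sites follow.

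A reader might infer more than the documents support:

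- *Early CNS toxicity is lost.* It is not. Under Section 11 safety reporting starts at the first dose, and Section 9.3 collects time to onset. The gap concerns the change score only, and the absolute PRO-CTCAE score at enrolment still shows symptoms present that day.
- *The endpoint is uninformative.* Change after enrolment can still be described. Only change from the untreated state is out of reach.
- *The schedule conflict causes the baseline problem.* The two are independent; settling one leaves the other.
- *The protocol plans a pooled final-visit mean over unequal follow-up.* It specifies no such analysis. The timing of that visit does vary, so its analysis needs care.

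**Conclusion.** Both defects hold. The on-treatment baseline affects every patient and follows from the visit definition and inclusion criterion 2 alone, without any assumption. How much early change it absorbs cannot be computed, because the protocol gives no onset times. The schedule contradiction is also explicit: five time points against about 7 to 10, with C1D15 unusable as a post-baseline point on 14 or, counting the same-day case, 15 of 22 enrolment days. Those are counts of permitted days, not of patients, since the distribution of enrolment days is unknown.

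The 28 to 53 day gap applies only under the 9.2/9.3 schedule. That gap and the mismatch of month and cycle labels rest on the assumed 28 to 30-day cycle. The endpoint is secondary, so this should be corrected before collection, but it does not threaten the primary safety objective.

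**What to change.** 1. State one questionnaire schedule identically in Sections 9.1, 9.2 and 9.3, anchored to the index date. Retain C2D1 as the early point, collect C1D15 only where it falls after enrolment, and reconcile the month and cycle labels.
2. Keep the final visit, but analyse it by time since first dose. Replacing it with fixed visits at months 18 and 24 would leave late enrolees with nothing after month 12.
3. Rename the first value *enrolment (on-treatment, 7–28 days after first dose)*. Report absolute scores and days since first dose alongside change.
4. Describe the result as change from an on-treatment value, not as the impact of lorlatinib, and add this limitation to Section 9.9.

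An optional pre-dose questionnaire is not recommended. It would move consent ahead of the baseline visit and create a selected subset with a different reference value.

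The cost is protocol wording, a few more electronic prompts than the five-visit schedule, and a more modest quality-of-life claim.
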